9.7 Procedure(s) to account for missing or spurious data

To assess the impact of study treatment on the evolution of QOL at week 48, we will use multiple imputation approach to replace missing values. We will compare the treatment effect on QOL on each of the 5 datasets generated, including the imputed values, and the results will be combined with Rubin's rules. A GEE model will be used. LOCF approach will be used to replace missing CD4 and CD8 values.

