9.3.3 Secondary outcome analysis

All secondary outcome analysis will be done with the ITT population. The p-values will be two-tailed, with a significant level of 0.05.

The proportion of patients with HIV-ribonucleic acid (RNA) viral load <50 copies/mL at week 48 will be analysed using the snapshot approach. Fisher's exact test will be used to compare the estimated proportion between the two groups.

A genotypic resistance test will be performed in all patients with virological failure. Drugs resistance mutations will be identified from the International AIDS Society (IAS)-USA resistance testing panel (last version at the time of analysis) and for BIC we will use IAS, Agence Nationale de Recherches sur le SIDA (National Agency for AIDS Research) (ANRS) or Royal College of Physicians (RCP) lists to perform the analysis whenever they will be made available. Resistance to BIC will also be identified using phenotypic resistance test. Fisher's exact test will be used to compare the presence of at least one drug resistance mutation between the 2 groups.

The median time to reach CD4 cell count >200/ μ l will be estimated using the Kaplan-Meier method, censoring at week 48 or last follow-up date if not seen at week 48. Time to reach CD4 cell count >200/ μ l will be defined as the time between the date of study treatment initiation (baseline, week 0) and the date of which patient reached CD4>200/ μ l. The log-rank test will be used to compare the two survival functions. The p-values will be two-tailed, with a significant level of 0.05. The proportion of patients with CD4 cell count <350/ μ l at week 48 will be done with the ITT population, with the last observation carried forward (LOCF) approach. Fisher's exact test will be used to compare the 2 groups.

The median change in CD4/CD8 ratio from baseline to week 48 will be analysed with the ITT population, with the LOCF approach. The non-parametric Mann Whitney test will be used to compare the change from baseline between the 2 groups.

The incidence of IRIS will be analysed with the Kaplan-Meier method. The Log-rank test will be used to compare the two survival functions. The effect of study treatment on IRIS will be assessed using Cox regression model with treatment group and adjustments for stratification factors.

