The incidence of hospitalisation will be estimated by the Kaplan-Meier estimate. The Log-rank test will be used to compare the two survival functions. The duration of hospitalisation will be estimated by the cumulative days of hospitalisation during the course of study and will be compared between the 2 groups by using the Mann-Whitney test. The rate of relapse/recurrence will be estimated by the number of patients with relapse/recurrence divided by the total number patients in ITT population. Fisher's exact test will be used to compare the 2 groups.

The frequency of each Grade 2, 3 or 4 AEs, laboratory toxicities, and ART and OI/BI treatment changes and dose modifications due to toxicities and IRIS will be described and compared by group. Fisher's exact test will be used to compare the 2 groups.

The proportion of patients with health care resource use, and emergency room visits will be compared in the two groups with Fisher's exact test. The total inpatient days will be estimated by the cumulative inpatient days during the course of study and will be compared between the 2 groups by using the Mann-Whitney test.

To assess the impact of study treatment on the evolution of QOL at week 48, we will use multiple imputation approach to replace missing values. We will compare the treatment effect on QOL on each of the 5 datasets generated, including the imputed values, and the results will be combined with Rubin's rules. A generalized estimating equation (GEE) model will be used.

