However, specifically regimens containing integrase inhibitors (INI) are promising candidates for treatment combinations in patients with CD4 cell counts $<200/\mu\text{l}$ due to their antiviral activity and rapid decline of viral load, beneficial side-effect profile and metabolism pathways compared to other regimens. Also, integrase inhibitors such as dolutegravir (DTG) and bictegravir (BIC/B) have high genetic barriers, thereby preventing resistance mutation development and ensuring sufficient antiviral activity in case of pre-existing mutations against nucleosides (Demarest *et al.*, 2018). Therefore, in cases when needs ART to be initiated before genotypic testing results are available, current European AIDS Clinical Society (EACS) Guidelines (EACS Treatment Guidelines 9.0) recommend to include a drug with a high genetic barrier to resistance in the first-line regimen (e.g. PI or DTG).

We therefore propose a strategic clinical trial to compare an INI containing regimen versus a boosted PI regimen in patients with advanced HIV-infection. We aimed to demonstrate the non-inferiority of an INI containing regimen [bictegravir (B) /emtricitabine (F) /tenofovir alafenamide (TAF) QD] versus a boosted PI regimen [darunavir (D) /cobicistat(C) /emtricitabine (F) /tenofovir alafenamide (TAF) QD] in patients with advanced HIV infection. The superiority of the INI-based treatment group over the PI-based treatment group will be assessed in the event that non-inferiority is established.

This Statistical Analysis Plan (SAP) details the different populations of analysis and the statistical methodology that will be used to analyse the data. It describes the efficacy and safety variables and anticipated data transformations and manipulations, and other details of the analyses not provided in the study protocol. The analyses described are based upon the clinical study protocol Version 2.0 dated 16 June 2020. This SAP will be validated and signed before the primary endpoint analysis is performed.

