5.3 HANDLING OF MISSING DATA

The primary and all secondary end points will be analysed on a mITT basis.

During the study, participants may be lost to follow-up, withdraw or drop out. A participant will be considered lost to follow-up if he/she is unreachable for at least two consecutive visits by the study site until the end of the study. And so, for these participants, observations will be censored from the date of last observation.

In addition, for participants still being followed in the study but whose observation is missing at week 48 and at the 30-day visit after week 48, data will be censored at the last observation.

Partial dates will be extrapolated. For example, all dates saved as NK/FEB/2020 will be recoded as 15/FEB/2020 and those saved NK/NK/2020 will be recoded as 30/JUNE/2020. NK means not known.

For the assessment of HIV RNA viral load reduction at week 12, we will use the last observation carried forward approach to fill in missing data at visit 12.

For all continuous variables used as endpoint, if the value is missing at week 48 and the value at the 30-day visit after week 48 is not missing, it will be used to replace the missing week 48 value whether or not the patient has been switched off the study drug.

For participants who stop the study prematurely, if the Early Termination Visit (ETV) is performed, the value will be used to complete the nearest missing visit.

For participants for whom the date of onset of the clinical event used as an endpoint is missing, the missing date of onset will be replaced by the event reporting date.

For patients reported outcomes, we will used multiple imputation approach to fill in missing data.

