10.1.3 Quality of life (EQ-5D-3L questionnaire) and HIV Symptoms index

Endpoints

The endpoints are:

- Change from baseline in health status score ranging from 0 to 100 (100 being best quality of life) and in each of the 5 dimensions of the EQ-5D-3L quality of life questionnaires (mobility, self-care, usual activities, pain/discomfort and anxiety/depression). Each dimension has 3 levels: 1=no problems, 2=some problems, and 3=extreme problems.
- Change from baseline in HIV symptoms index score over time. HIV Symptoms Index questionnaire is consisted of 20 selected symptoms. Each symptom has 5 levels: 0=I do not have this symptom 1=It doesn't bother me 2=It bothers me a little 3=It bothers me 4=It bothers me a lot. The HIV Symptom Index score is the sum of frequency ratings for the 20 selected symptoms; the score could range from 0 to 80.

Descriptive statistics and graphical representation

The analyses will be performed with the mITT population who complete the baseline questionnaire and least one of the follow-up questionnaires.

Data for health status score and HIV Symptoms index will be summarised by mean and standard error. The evolution of health status score and HIV Symptoms index will be described by boxplots for each treatment group at each time point.

Data for the 5 dimensions will be summarised with number and percentages per class and Bar plotted will also be generated for each of the 5 dimensions.

The number of participants with data available at each time point will also be reported.

Statistical methodology

The changes from baseline in health status score will be compared between the two treatment groups using mixed models for repeated measures with random intercept and slope and spatial power covariance structure due to unequal time intervals between visits, adjusted for country/group of neighbouring countries and baseline CD4 cell counts (<50 or $\geq 50/\mu\text{L}$). The model will include treatment group, time, interaction between treatment group and time, country/group of neighbouring countries and baseline CD4 cell counts (<50 or $\geq 50/\mu\text{L}$). Time will be modelled as categorical variables.

The distribution of each of the 5 dimensions (mobility, self- care, usual activities, pain/discomfort and anxiety/depression), will be compared between the two treatment groups at each timepoint using Chi-square test

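### The protocol specifies only 5 imputed datasets for quality of life and the SAP gives no number or seed; at least 50 with a recorded seed would stop borderline results depending on the random draw, at no cost beyond computing time.

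*Combined protocol and SAP*

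**What the plan says.** Protocol v5.0, section 9.3.3: "We will compare the treatment effect on QOL on each of the 5 datasets generated", with the results combined by Rubin's rules. Section 9.7 repeats the instruction ("on each of the 5 datasets generated") and adds "A GEE model will be used". Protocol v1.5 has the same text. Secondary outcomes are tested at the usual level: "The p-values will be two-tailed, with a significant level of 0.05".

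SAP v0.3, section 5.3: "For patients reported outcomes, we will used multiple imputation approach to fill in missing data". It gives no number of datasets, imputation model or seed. SAP 10.1.3 restricts the analysis to the "mITT population who complete the baseline questionnaire and least one of the follow-up questionnaires". It compares the EQ-5D health status score and the HIV Symptom Index "using mixed models for repeated measures with random intercept and slope", and mentions neither 5 datasets, nor Rubin's rules, nor GEE.

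On dates, the SAP (22 November 2023) says "The analyses described are based upon the clinical study protocol Version 2.0 dated 16 June 2020". Protocol v5.0 (11 March 2024) is later and still carries the 5. It is the only number of imputations given anywhere in the documents.

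**The concern.** Multiple imputation replaces each missing value with random draws. With few datasets, two things go wrong. First, the between-imputation variance is estimated on only 4 degrees of freedom, and Rubin's rules pay for this with a wider interval. Second, the pooled estimate and its standard error carry simulation noise, so the same code run on the same data with another seed gives a different p-value.

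The week-48 quality-of-life comparison is a listed secondary endpoint in an open-label trial. If its p-value falls anywhere near 0.05, the reported conclusion could depend on an unrecorded random draw. A second analyst following the plan exactly might not reproduce it.

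**Working it through.** **Inputs from the documents.** Number of imputations m = 5 (protocol 9.3.3 and 9.7). Two-sided level 0.05 (protocol 9.3.3). The plan states no precision figure for quality of life and no FMI. The only related rate is the roughly 7.5% per year dropout in protocol 9.1, where 404 / (1 − 0.075) = 437, against 440 planned.

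**Assumption.** FMI is taken as 0.075 (equal to the dropout rate), 0.20, 0.30 and 0.40. None of these is a document value for quality of life.

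**Step 1: interval width.** Scale the many-imputation variance to W + B = 1, where W is the within-imputation and B the between-imputation variance, so that B = FMI. Then:

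- T = W + (1 + 1/m)B = 1 + FMI/m
- λ = (1 + 1/m)B / T
- df = (m − 1)/λ²
- width ratio = √T × t(0.975, df) / 1.960

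Example with m = 5 and FMI 0.20: T = 1.04; √T = 1.0198; λ = 0.24/1.04 = 0.2308; df = 4/0.0533 = 75; t = 1.992. The ratio is 1.0198 × 1.992/1.960 = 1.037.

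Example with m = 50 and FMI 0.20: T = 1.004; √T = 1.0020; df = 1187; t = 1.962. The ratio is 1.003.

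| FMI | df, m = 5 | widening, m = 5 | widening, m = 50 |
|---|---|---|---|
| 0.075 | 509 | 1.0% | 0.1% |
| 0.20 | 75 | 3.7% | 0.3% |
| 0.30 | 35 | 6.7% | 0.5% |
| 0.40 | 20 | 10.5% | 0.8% |

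The Barnard-Rubin small-sample degrees of freedom give almost the same widths.

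**Step 2: noise in the estimate.** The Monte Carlo standard deviation of the pooled estimate, in units of its standard error, is √(FMI/m).

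- m = 5: √(0.075/5) = 0.12 and √(0.20/5) = 0.20
- m = 50: 0.04 and 0.06

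**Step 3: what this does to the p-value.** Imputation sets were simulated with the many-imputation p-value held fixed. Both the pooled estimate and the between-imputation variance were allowed to vary, and p was read from the t distribution with Rubin's degrees of freedom.

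Many-imputation p = 0.05, 95% range over seeds:

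| FMI | m = 5 | m = 50 |
|---|---|---|
| 0.075 | 0.027 to 0.094 | 0.041 to 0.061 |
| 0.20 | 0.016 to 0.154 | 0.035 to 0.070 |

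Many-imputation p = 0.03, chance that a single run gives p > 0.05:

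| FMI | m = 5 | m = 50 |
|---|---|---|
| 0.075 | 9% | about 0% |
| 0.20 | 29% | 0.4% |

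The second table is the fairer test. A result sitting exactly at 0.05 will fall on either side with any number of imputations, whereas one at 0.03 should not.

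**The case against.** **Size of the widening.** A reader might infer that the quality-of-life intervals will be 4% to 10% too wide. The documents do not support that. A 4% widening needs an FMI of about 0.21 and 10% needs about 0.39, and no such value is given. Several features push FMI down. The questionnaires are collected at baseline, six treatment visits and the 30-day follow-up, so neighbouring visits inform week 48. SAP 5.3 fills a missing week-48 continuous value from the 30-day visit, and uses the early-termination value for the nearest missing visit. SAP 10.1.3 drops participants without a baseline and at least one follow-up questionnaire. In the other direction, people still in the trial can skip questionnaires. This part of the objection stands: the widening can be given only as a range, and its low end is about 1%.

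**Whether 5 is still the plan.** A reader might also take the SAP's silence as confirming 5. It does not. The SAP states no number and replaces the protocol's GEE with a mixed model, so it does not simply inherit the protocol's sentence. The number actually intended is open, which is a reason to state it. If the sponsor means the mixed model to be fitted to the observed scores without imputation, the number of datasets ceases to matter for those scores, but SAP 5.3 would then have to say so.

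**Validity and consequence.** Intervals from 5 datasets under Rubin's rules are valid; they are only less efficient. The endpoint is secondary, the primary analysis does not use imputed quality-of-life data, and a result far from 0.05 would not cross. All of this stands and limits the point to a minor one. It does not answer the seed dependence, which is material even at FMI 0.075.

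**Conclusion.** The point holds as a minor, free improvement. The protocol names 5 datasets and the SAP names neither a number nor a seed. The loss of precision is between about 1% (FMI 0.075) and 10.5% (FMI 0.40) of interval width, depending on an FMI that the documents do not give. The firmer reason to change is reproducibility. Over the FMI range 0.075 to 0.20, a comparison whose settled p-value is 0.03 would be reported as non-significant in 9% to 29% of single runs with 5 datasets, against under 1% with 50. These figures assume Rubin's rules with the usual degrees of freedom and a limiting p-value near 0.05. They say nothing against the validity of the intervals and have no bearing on the primary non-inferiority comparison.

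**What to change.** Before the SAP is signed off (SAP 5.1 already provides for an update at that stage):

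- State in SAP 5.3 and 10.1.3 that at least 50 imputed datasets will be used, replacing the protocol's 5, with a fixed and recorded seed. Name the imputation model there too.
- State which analysis is applied to the imputed data, reconciling the protocol's GEE with the SAP's mixed model.
- Record the change as a deviation in the way protocol 9.8 provides, or align protocol 9.3.3 and 9.7 at the next amendment. An amendment for this alone is not needed.

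The cost is a few lines of SAP text and some computing time. No extra patients, visits or data are required.

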5. GENERAL CONSIDERATIONS

All continuous variables will be summarised using the following descriptive statistics: n (non-missing sample size), mean, standard deviation (SD), 1st quartile, median, 3rd quartile, maximum and minimum. The frequency and percentages (based on the non-missing sample size) of observed levels will be reported for all categorical variables.

The number of participants and the flowchart of the study will be presented. The period of enrolment and the total number of participants screened to be included in the study will be presented. The number of ineligible participants and the total number of randomized participants will be presented.

The number of participants who never receive the study intervention will also be presented by treatment group and those who were included in the full analysis set and the safety analysis set will be presented.

Baseline is considered as the day 1 visit and the baseline data is data collected just before intervention at day 1.

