5.2.1 Full Analysis Population

Modified Intention-to-treat (mITT) analysis set: all randomised participants who received at least one dose of study drug. Participants will be included in the analyses according to the planned randomised intervention.

The following data points sets are defined:

- **DPS1:** All observed data will be included in the analysis set regardless of study intervention discontinuation and/or receipt of rescue therapy
- **DPS2:** For participants who discontinue study intervention and/or receive rescue therapy, post-discontinuation or post-rescue observations will be excluded.

The mITT and DPS1 will be used to estimate the primary endpoints and the all secondary endpoints.

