The evolution of the proportion of participants with CD4<200/ μ L and <350/ μ L over time will be compared between the 2 treatment groups (DRV/c versus BIC) using a Generalized Estimating Equation (GEE) models with independent covariance structure, binomial distribution and log link, to estimate the relative risk. The models will include treatment group, time, and interaction between treatment group and time. Time will be modelled as categorical variable. A relative risk (RR) and the associated 95% CI will be calculated. All P-values will be two-tailed with a significant level at 5%.

7.2.6 Change in CD4/CD8 ratio from baseline to week 48

Endpoints

The change in CD4/CD8 ratio from baseline to week 48.

Descriptive statistics and graphical representation

The analyses will be performed with the mITT population and DPS1. Data will be summarized in tables by mean and standard error. The evolution of CD4/CD8 ratio will be described by boxplots for each treatment group at each time point. The number of participants with data available at each time point will also be reported.

Statistical methodology

The mean change in CD4/CD8 ratio from baseline to week 48 will be compared between the 2 treatment groups using a mixed model with random intercept and slope and spatial power covariance structure due to unequal time intervals between visits. The models included treatment group, time, and interaction between treatment group and time. Time was modelled as a categorical variable. All P-values will be two-tailed with a significant level at 5%.

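### Protocol v5.0 carries the last CD4 and CD8 values forward, while the SAP analyses the same secondary endpoints on observed data; one missing-data rule should be fixed before sign-off

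*Combined protocol and SAP*

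**What the plan says.** **Protocol v5.0 (March 2024).** Section 9.7 gives a general rule: "LOCF approach will be used to replace missing CD4 and CD8 values". Section 9.3.3 applies it to two analyses. The first is the CD4 proportion below 350, which "at week 48 will be done with the ITT population, with the last observation carried forward (LOCF) approach", compared by Fisher's exact test. The second is the CD4/CD8 change from baseline to week 48, compared by the Mann-Whitney test. Section 9.3.3 describes no analysis of the proportion below 200, although that is a listed endpoint. For that threshold the carry-forward rule rests on the general sentence in 9.7.

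**SAP v0.3 (November 2023, written to protocol v2.0).** Section 7.2.5 analyses the proportions below 200 and below 350 at all visits with GEE "models with independent covariance structure, binomial distribution and log link, to estimate the relative risk". The model terms are treatment, time and their interaction. Section 7.2.6 uses a mixed model for CD4/CD8. Both use the data set defined in 5.2.1: "All observed data will be included in the analysis set regardless of study intervention discontinuation and/or receipt of rescue therapy". Section 5 sets the denominator: "The frequency and percentages (based on the non-missing sample size) of observed levels will be reported for all categorical variables".

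**SAP 5.3 on missing data.** Carry-forward is named once: "For the assessment of HIV RNA viral load reduction at week 12, we will use the last observation carried forward approach". Two other rules can reach CD4. If the week-48 value of a continuous endpoint variable is missing and a value exists from the visit 30 days later, "it will be used to replace the missing week 48 value whether or not the patient has been switched off the study drug". For patients who stop the study early, an early termination visit value fills the nearest missing visit. Multiple imputation is reserved for one class of outcome: "For patients reported outcomes, we will used multiple imputation approach to fill in missing data".

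**The concern.** Immunological response is a stated secondary objective, and the two documents handle a missing CD4 value differently. A patient who leaves after week 12 and does not return has a week-48 value under the protocol (the week-12 value) and none under the SAP.

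The choice is not neutral, because CD4 is expected to rise. Many participants qualify with a count below 100 or below 200. Protocol 1.2.1 quotes mean week-48 gains of 201 to 229 cells from two earlier treatment-naïve studies, though in a less advanced population. An early value carried to week 48 therefore tends to count the leaver as unrecovered, and an arm that loses more patients early would look worse partly for that reason.

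The SAP rule has its own condition. An unweighted independence GEE on available values generally requires drop-out to be unrelated to earlier CD4, given what is in the model. The model in 7.2.5 has no baseline CD4 term.

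The trial is open-label, and SAP 5.1 allows the SAP to be updated after the statistician has reviewed a mock-up report on a temporary database. Two standing rules for one endpoint leave room for a choice made after data have been seen.

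**Working it through.** **Inputs from the documents** (sample-size sections of protocol and SAP): drop-off about 7.5% per year; 202 evaluable and 220 enrolled per arm.

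**The plan's own figure.** 202/(1 - 0.075) = 218.4, so 219 per arm against the stated 220. The figure reproduces, and d = 0.075 (0.075 × 220 = 16.5 patients per arm) is a fair reading of the plan.

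**Assumed, because the documents do not give them.** p is the share of observed patients below the threshold at week 48. q is the share of leavers whose last CD4 is below it.

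**Distance between the two rules in one arm**
- Carry-forward: (1 - d)p + dq. Observed data: p. Difference: d(q - p).
- Standard error of the observed proportion: sqrt[p(1 - p)/(220(1 - d))].
- Example, p = 0.40, q = 0.80: 0.075 × 0.40 = 3.0 points. SE = sqrt(0.24/203.5) = 3.43 points. Ratio 0.87.

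Difference in points (per-arm SE) at d = 7.5%:

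| p | q = 0.60 | q = 0.80 | q = 1.00 |
|---|---|---|---|
| 0.20 | 3.0 (1.07) | 4.5 (1.60) | 6.0 (2.14) |
| 0.30 | 2.25 (0.70) | 3.75 (1.17) | 5.25 (1.63) |
| 0.40 | 1.5 (0.44) | 3.0 (0.87) | 4.5 (1.31) |
| 0.50 | 0.75 (0.21) | 2.25 (0.64) | 3.75 (1.07) |
| 0.60 | 0 (0) | 1.5 (0.44) | 3.0 (0.87) |

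A difference of exactly one SE needs q = 0.57, 0.73, 0.86 or 0.97 at p = 0.20, 0.30, 0.40 or 0.50. It cannot occur at p = 0.60.

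**Effect of the SAP 5.3 fill-in rules.** Suppose they recover half of the leavers' week-48 values, with a share q of those below the threshold. At p = 0.40, q = 0.80 the ratio falls from 0.87 to 0.43 SE.

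**Treatment contrast** (q = 0.80; movement scaled to the SE of the risk difference, 4.7 to 4.9 points):

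| Drop-out, arm 1 v arm 2 | p, arm 1 v arm 2 | Risk difference, observed → carried forward | Movement | Relative risk |
|---|---|---|---|---|
| 7.5% v 7.5% | 0.40 v 0.45 | -5.0 → -4.6 points | 0.08 SE | 0.889 → 0.903 |
| 7.5% v 7.5% | 0.30 v 0.40 | -10.0 → -9.25 points | 0.16 SE | 0.750 → 0.785 |
| 5% v 10% | 0.40 v 0.40 | 0 → -2.0 points | 0.41 SE | 1.000 → 0.955 |
| 5% v 10% | 0.40 v 0.45 | -5.0 → -6.5 points | 0.31 SE | 0.889 → 0.866 |
| 10% v 5% | 0.30 v 0.40 | -10.0 → -7.0 points | 0.64 SE | 0.750 → 0.833 |

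With equal d and q in both arms, carry-forward multiplies the risk difference by (1 - d) = 0.925, which is why it hardly moves. The 5% and 10% rates are illustrative; no document suggests unequal drop-out.

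**The case against.** The strongest reply is that this is old wording rather than a live dispute. The carry-forward sentence is unchanged since protocol v1.5, and the only logged change from v4.0 to v5.0 concerns data protection. The later date of v5.0 might be read as a fresh decision in favour of carry-forward; the amendment log does not support that. The SAP is the more detailed document and is still to be finalised, and protocol 9.8 already provides for recording deviations and amending for major changes. All of this stands, but it explains the conflict without resolving it. No text says which rule governs.

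A second reply is that the SAP already limits the loss. Patients who stop study drug are followed to week 48, their data are kept, and the two fill-in rules recover some values. A reader might infer that the SAP uses only available CD4 values; SAP 5.3 shows otherwise. It remains unclear whether the 30-day rule, written for continuous variables, reaches a dichotomised CD4 endpoint.

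A third reply is that nothing shows the SAP's GEE to be biased. That also stands. In a simulated CD4 course with drop-out spread evenly over visits (assumed baseline median 45, 38.0% below 200 at week 48), available data gave 37.9% and carry-forward 41.0%. Drop-out that depends on CD4 was not tested. This supports imputation as a sensitivity analysis; it does not support requiring it as the main analysis.

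**Conclusion.** The conflict holds and should be resolved before the SAP is signed. Carry-forward is the weaker rule for a count expected to rise, so it is the one to remove.

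The size depends on assumptions. Only the 7.5% and the 220 per arm come from the documents. Over p = 0.20 to 0.60 and q from p to 1.00, the two rules differ within an arm by 0 to about 2 standard errors. A reader might infer that they differ by about one standard error. That is one point in the range, and the documents give neither the week-48 proportion nor the leavers' CD4. The formula measures the distance between the rules. It equals the bias of carry-forward only if leavers would have reached week 48 with the same proportion below the threshold as those observed.

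A reader might also infer that the treatment comparison is materially distorted. With equal drop-out it moves by at most 0.16 SE in the cases tried. At 5% against 10% it moves by about 0.3 to 0.6 SE, which is modest. The conflict is explicit for the proportion below 350 and for CD4/CD8; for the proportion below 200 it rests on the general sentence in 9.7. The primary endpoint is not built on these CD4 endpoints.

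**What to change.** 1. Delete carry-forward for CD4 and CD8 from protocol 9.3.3 and 9.7. Alternatively, state that the SAP supersedes those sentences and record the change as protocol 9.8 requires.
2. Keep the SAP mixed model for CD4/CD8 and the GEE for the CD4 proportions.
3. State in SAP 5.3 whether the 30-day rule applies to dichotomised CD4.
4. Add to SAP 7.2.5 a sensitivity analysis with multiple imputation of missing CD4 from earlier CD4, viral load and arm. CD4 is scheduled at every visit, and the SAP already plans multiple imputation for patient-reported outcomes.

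The cost is a wording amendment and a little more programming. If the protocol text itself is changed, both the UK (v4.0) and EU (v5.0) versions need attention, with submission to ethics committees and regulators if the sponsor classes the amendment as substantial. The second option in item 1 may be lighter if the change is not classed as major.
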